1.2 Sources of Materials

Research material obtained from the participants include responses to in-person and telephone-based questionnaires regarding smoking patterns, attitudes, behaviors, etc. Research data will be obtained specifically for research purposes. There will be no use of existing specimens. The consent form will include language to allow access to the participant's Electronic Medical Record (EMR) data, for up to 2 years following date of consent. Every effort will be made to maintain subject confidentiality, in accordance with HIPAA.

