4.1 Summary of the Protocol

The design calls for a 2-group, randomized clinical trial of 1) standard care (Ask, Advise, Refer) vs. 2) standard care + NRT sampling. Randomization will be at the clinic level, but the unit of analysis is the individual smoker. Following consent, baseline assessment, and provider intervention (all done within clinic), follow-up assessment (coordinated centrally through our study team) will continue at +1, +3, and +6 months. The primary outcome will be 7-day point prevalence abstinence at 6-month follow-up, though we track a number of other outcomes as well. A recent trial of comparative effectiveness for single/combined pharmacotherapy (79) provided strong framework for our decisions. As a comparative effectiveness study, our guiding philosophy is to optimize ecological (i.e., external) validity, while at the same time maintaining basic standards of scientific rigor.

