4.2 Primary and secondary outcomes

The primary outcome on which our study is powered is 7-day point prevalence at 6 month follow-up, which, unlike continuous abstinence, allows for delayed quitting. Unlike traditional cessation trials, there is no uniform quit date for all participants in the current trial, and thus anchoring abstinence to a designated quit attempt is unrealistic. However, we will track a number of secondary outcomes, including 30-day point prevalence abstinence, and incidence, frequency, latency, and duration of quit attempts (both self-defined and those lasting >24hrs), as well as smoking reduction (% reaching 50% reduction between baseline and end-of-study), provider acceptability and cost-effectiveness.

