Cost Effectiveness We will track intervention delivery costs (i.e., personnel, materials, NRT itself) per treatment group, though anticipate the only difference to be the cost of NRT. We will analyze and compare costs for intervention and control patients, for quit attempters vs. non-quit attempters, and for quitters vs. non-quitters. We will do this both across and within groups, and our model will adjust for patient characteristics, including demographics and smoking history. Led by our dissemination expert ([name]), we will examine differences in direct medical costs (from the EMR) of all medical care post study enrollment for a sample of all study participants, of all participants who quit smoking during the trial, and for all intervention participants. We expect to show that NRT sampling as a strategy is, at least in the short term cost neutral, if not cost saving.

Other We will also examine changes in cigarette smoking, motivation, confidence, attitudes/knowledge of NRT over time, as a function of treatment group. These continuous variables (absolute, and change since baseline) will be examined as per Hypothesis 1b above.

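### Costs by quit status are counted from enrolment although quitting comes later, so pre-quit costs are booked to quitters: any true saving is diluted, and illness that prompts a quit is charged to the quitter group

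*Combined protocol and SAP*

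**What the plan says.** The Cost Effectiveness paragraph of section 4.9 plans to compare costs between the two arms and also "for quit attempters vs. non-quit attempters, and for quitters vs. non-quitters". Medical costs are defined two sentences later as "direct medical costs (from the EMR) of all medical care post study enrollment", to be examined in a sample of participants, in the intervention participants, and in the group "of all participants who quit smoking during the trial". On confounding it says that "our model will adjust for patient characteristics, including demographics and smoking history".

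Section 4.2 states that "there is no uniform quit date for all participants in the current trial" and that the chosen abstinence endpoint, "unlike continuous abstinence, allows for delayed quitting". Under section 4.1, follow-up assessment "will continue at +1, +3, and +6 months". Section 1.2 allows access to the medical record "for up to 2 years following date of consent".

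No section gives a quit-date anchor, a landmark time, a time-varying quit status or an adjustment for earlier costs. The length of the cost window and the definition of a quitter for this analysis are also not given.

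**The concern.** The groups are formed by something that happens after enrolment, but the cost clock starts at enrolment. Two distortions can follow.

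- **Dilution.** Months in which an eventual quitter was still smoking count as quitter cost. Any real reduction after quitting is averaged with time in which it could not yet occur.
- **Reverse causation.** A hospital stay or new diagnosis that leads someone to quit is charged to the quitter group, although it came before the quit and may have caused it.

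Adjusting for demographics and smoking history does not address either one, because the difficulty is the order of cost and quit in time. The contrast of attempters with non-attempters has the same structure. At stake is the size, and in some settings the sign, of a non-randomised contrast within cost-effectiveness, which section 4.2 lists as a secondary outcome.

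**Working it through.** The plan gives no cost, effect size or power figure for this analysis, so there is nothing to reproduce. The checks below use the plan's time structure and stated assumptions.

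**Inputs from the documents.** Costs run from enrolment (4.9). Status is assessed at 1, 3 and 6 months (4.1). Record access lasts at most 24 months (1.2). The projected base quit rate is 15% (2.2.5 and 4.13).

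**Step 1: dilution.** Pre-quit share = mean month of quitting / length of cost window. With even monthly costs, the observed difference = true difference × (1 − share). The quit timings are assumptions.

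| Quit timing | 6-month window | 12-month window | 24-month window |
|---|---|---|---|
| Even over months 0-6 (mean 3) | 3/6 = 50% | 3/12 = 25% | 3/24 = 12.5% |
| Early (mean 1) | 1/6 = 17% | 1/12 = 8% | 1/24 = 4% |

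An extreme case is the participant who stops at the start of the 7 days before the 6-month call and counts as abstinent. The share is (6 − 7/30.4)/6 = 96% of a 6-month window, and 24% of a 24-month one.

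For a true 20% post-quit saving and evenly spread quits, the formula gives an observed saving of 20% × 0.50 = 10% at 6 months and 20% × 0.875 = 17.5% at 24 months. Monthly simulations in which the saving starts the month after the quit gave about 8-9% and 17%.

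**Step 2: illness that prompts quitting, no true effect on cost.** The assumptions, none from the documents except the 15%, are $300 per month, a 1% monthly chance of a $10,000 hospital stay, 15% quitting over 6 months, and a higher chance of quitting in a month with a stay. The false excess in quitter cost is:

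| Stay multiplies chance of quitting by | 6-month window | 24-month window |
|---|---|---|
| 2 | 4.4% | 1.2% |
| 3 | 8.8% | 2.3% |

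A second set of assumptions (a 3% monthly chance of an event costing 20 times the monthly base) gave 7% at 6 months and 1% at 24 months for a multiplier of 2, and 20% and about 5% for a multiplier of 4. The direction is stable; the size depends on inputs that the documents do not supply.

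**Step 3: both together.** Under the second set, with a true cost ratio of 0.80 and a multiplier of 4, the contrast from enrolment gave 1.10 at 6 months (wrong sign), 0.95 at 12 and 0.87 at 24.

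**Step 4: neither.** With no effect of quitting on cost and no link from illness to quitting, the ratio was about 1.00 in every window.

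**Step 5: does the remedy work?** Under the second set, classifying at month 6 and counting costs afterwards returned 0.80 when the truth was 0.80 and 0.99-1.00 when it was 1.0 (12- and 24-month windows). Splitting person-months at the quit did the same in all windows. Those runs treat illness as independent from month to month. Under the Step 2 costs, if one stay raises later monthly risk fivefold, the bare landmark leaves a false excess of about 4% (multiplier 6) to 7% (multiplier 9). Adjusting for costs before the call brings it to about zero.

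**The case against.** The strongest reply is textual. The contrast by quit status directly follows the sentence on intervention delivery costs and says only costs. The medical-record sentence comes later and names no non-quitter or attempter group, and its enrolment wording might merely bound which records are pulled. It is fair that the plan leaves the link implicit. But the sentences form one paragraph, quitters are named in the medical-cost sentence, and no other start point is offered. Followed as written, the rule counts pre-quit cost.

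A second reply is that dilution is an error only if the target is cost after quitting. For total cost since enrolment among eventual quitters, the early months belong in the total. The plan does not state the target. That stands, and is a reason to state it.

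Third, the numbers rest on assumptions. Advice and samples are given at baseline, so quits may cluster early, where the 24-month loss is only 4%. Long windows may also be common: if enrolment follows the timetable in section 4.6, 754/1300 = 58% will have 24 months of record by month 60 and 986/1300 = 76% at least 12 months. Only the last enrollees (month 50) would be limited to 10. This stands as a limit on size.

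A reader might also infer that the plan's expectation of short-term cost neutrality or saving is undermined. It is not: that expectation concerns sampling as a strategy, which is the contrast of randomised arms, and enrolment is the correct start for it.

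**Conclusion.** The point holds in a conditional form. Costs counted from enrolment dilute a true post-quit saving by the pre-quit share of the window: about 50% at 6 months and 12.5% at 24 months if quits are evenly spread, 17% and 4% if they average month 1. If illness prompts quitting, quitters look falsely costly, illustratively by 4-9% at 6 months and 1-2% at 24 months for a doubled or tripled chance of quitting. The documents do not allow that amount to be fixed.

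A reader might infer that the contrast is biased whatever the truth, or that quitters would look a quarter or more too costly. The documents support neither. Without an effect of quitting on cost or a link from illness to quitting there is no bias, and excesses of that size need a link far stronger than anything the documents support. The primary outcome and the comparison of arms are untouched. This is a cheap improvement of low severity.

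**What to change.** Add two or three sentences to the Cost Effectiveness paragraph of section 4.9, for the quit-status and quit-attempt contrasts only:

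- Define quitter and attempter for this analysis, and state the cost window and its start.
- Either classify participants at the 6-month call and count medical-record costs from that call over a fixed window, adjusting for costs before the call, or treat quit status as time-varying so that person-months before the quit count as smoking time. The consented 2 years leave up to 24 − 6 = 18 months after the call.
- Label these contrasts observational.
- Keep the enrolment clock for the comparison of randomised arms.

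The data are already planned: record dates, latency of quit attempts (section 4.2) and the 6-month call. The cost is a little more analysis. The landmark version drops the first 6 months, although the plan has a short-term interest, and is less precise for late enrollees: someone starting in month 50 has the call at month 56 and only 60 − 56 = 4 months of later record if records are pulled at month 60. A later pull using the full consented period, or the time-varying version, eases this.

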4.4 Sample Size

The sample size is 1300 participants. Section C.10 of the grant text provides a detailed rationale for why this sample size was chosen.

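### Cost-effectiveness is a named secondary outcome, but the plan only compares costs: it relates no cost difference to the abstinence difference and sets no criterion for cost neutrality

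*Combined protocol and SAP*

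**What the plan says.** Section 4.2 (Primary and secondary outcomes) ends its list of secondary outcomes with "provider acceptability and cost-effectiveness".

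The method is in Section 4.9, Secondary Analyses, under Cost Effectiveness:

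- Delivery costs are tracked by treatment group, "though anticipate the only difference to be the cost of NRT".
- The comparisons are: "We will analyze and compare costs for intervention and control patients, for quit attempters vs. non-quit attempters, and for quitters vs. non-quitters".
- On modelling, "our model will adjust for patient characteristics, including demographics and smoking history".
- Direct medical costs from the electronic record are examined "for a sample of all study participants, of all participants who quit smoking during the trial, and for all intervention participants".
- The stated expectation is: "We expect to show that NRT sampling as a strategy is, at least in the short term cost neutral, if not cost saving".

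Section 1.2 allows access to the electronic record "for up to 2 years following date of consent". The Specific Aims and Section 4.1 place randomisation at the clinic level.

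**The concern.** A cost-effectiveness result relates what a strategy adds in cost to what it adds in effect. Each contrast in the paragraph has cost alone as its outcome. Someone who followed the plan to the letter would finish with several cost differences and no statement of what one more abstainer costs.

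The second gap is the neutrality expectation. To show that two strategies cost the same, one needs a margin and an interval narrow enough to fit inside it. The plan has neither. Medical costs usually vary widely between patients, so a difference that is not significant may still be compatible with a material rise.

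At stake is whether a named secondary outcome is delivered, and whether a statement about cost neutrality could be defended if it were made. The primary abstinence analysis is not affected.

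**Working it through.** **1. The outcome against the analysis.** An incremental cost-effectiveness result needs four quantities: mean cost and abstinence rate in each arm. Section 4.9 provides for delivery cost by group in the cost paragraph, and for abstinence rates with 95% confidence intervals under Hypotheses 1a, 2 and 3. It does not combine them. No incremental ratio, net benefit, perspective, time horizon or method for joint uncertainty is given.

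**2. Where neutrality would have to come from.** The plan anticipates that delivery cost will differ only by the cost of NRT, which puts the sampling arm higher. Overall neutrality therefore requires an offset in medical cost. The sets named for medical costs overlap: a sample of everyone, those who quit, and the whole intervention arm. No size is given for the sample and no control-arm set is defined. The short term is not defined either, although record access runs to 2 years.

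**3. Clustering.** Section 4.9 specifies GEE by clinic for Hypotheses 1a, 1b, 2 and 3, and carries the 1b method to the smoking, motivation, confidence and attitude measures under Other. For costs it mentions only adjustment for patient characteristics.

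**4. Attainable precision (illustration).** The documents give no cost variance, margin or power for costs, so there is no figure of the plan's to reproduce.

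Inputs from the documents: 1300 participants (Section 4.4), about half in each arm and 20 clinics (Specific Aims). That gives 650 per arm and 1300/20 = 65 per clinic. Assumed: coefficient of variation of cost (CV) 1 to 3, intraclass correlation (ICC) 0 or 0.01, and every participant costed.

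- Design effect: DE = 1 + (65 − 1) × ICC, which is 1 at ICC 0 and 1.64 at ICC 0.01.
- 95% half-width as a percentage of mean cost = 100 × 1.96 × CV × √(2 × DE / 650).

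| Assumed CV | ICC 0 | ICC 0.01 |
|---|---|---|
| 1 | ±10.9% | ±13.9% |
| 2 | ±21.7% | ±27.8% |
| 3 | ±32.6% | ±41.8% |

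With a t multiplier on 18 degrees of freedom (20 clinics less 2), the extremes become ±11.7% and ±44.8%. Costing only a sample widens every entry.

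**5. Size needed to exclude a rise (illustration).** For one-sided 0.025, 80% power, no true difference and no clustering, n per arm = 2 × [CV × (1.960 + 0.842) / margin]². For a 10% margin this gives 1570 at CV 1 and 6280 at CV 2. For a 20% margin at CV 1 it gives 393, which 650 per arm meets without clustering.

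**6. The missing estimate.** Cost per additional abstainer = (difference in mean cost) / (difference in abstinence). The documents give a projected base rate of 15% (Section 4.13) but no expected gain; Section 4.4 refers to grant text for the sample-size rationale. For assumed gains of 3, 5 and 7 points, each dollar of added cost per participant becomes 1/0.03 = 33, 1/0.05 = 20 and 1/0.07 = 14 dollars per additional abstainer.

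**The case against.** The strongest reply has four parts.

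*The plan states an expectation, not a rule.* A reader might infer that any non-significant cost difference will be declared neutral. The documents do not say so. The cost paragraph gives no test, significance level or decision rule, and the one-sided 0.025 Wald test in Section 4.9 belongs to Hypotheses 1a, 2 and 3. This stands. The supportable statement is that nothing in the plan prevents that reading.

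*The policy case does not rest on cost.* A reader might infer that it does. The Project Narrative ties policy significance to smoking outcomes, the Specific Aims to a brief and acceptable strategy, and Section 3 to the hypothesised outcomes, ease of use and reach. This stands, and it limits the weight of the point.

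*The figures are assumed.* CV, ICC, margin and gain in abstinence are not in the documents, and 650 per arm does not describe a medical-cost sample of unstated size. This stands too, so the figures are illustrative. Sampling, however, can only make the precision worse, and the two structural gaps depend on none of these values.

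*The inputs are there.* Delivery cost and abstinence by arm are both planned, so a point estimate is simple division. True, but the plan does not commit to it or give its uncertainty. The quitter contrasts are not offered as a substitute and could not serve as one: quit status arises after randomisation, and adjusting for patient characteristics does not restore a randomised comparison.

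**Conclusion.** The point holds in a limited form. The cost analysis does not produce the secondary outcome that Section 4.2 names, and the neutrality expectation has no margin or interval criterion behind it. Both follow from the text alone.

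The size is illustrative: with all 1300 costed, the arm difference would be known to within about 11% to 42% of mean cost, for an assumed CV of 1 to 3 and ICC of 0 to 0.01. On those assumptions a null result would not by itself establish neutrality. The documents do not support saying that the trial will misread such a result, only that it could.

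This is a secondary analysis and no figure in the plan is contradicted. The text should be amended before analysis, but the point does not bear on the primary conclusion.

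**What to change.** Amend the Cost Effectiveness paragraph of Section 4.9 as follows.

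- **Main economic result.** Report the arm-level incremental delivery cost per additional participant with 7-day abstinence at 6 months: (mean cost, sampling − mean cost, standard care) / (abstinence, sampling − abstinence, standard care). State the perspective.
- **Uncertainty.** Use net-benefit regression clustered by clinic, over a stated range of values per abstainer, with a small-sample correction for about 20 clinics. This is preferable to a confidence interval for the ratio, which is unstable if the abstinence difference is near zero.
- **Medical costs.** Compare the randomised arms over a fixed horizon, with the same sampling in both arms and the sample size stated. Account for clinic clustering.
- **Neutrality.** Replace the expectation with: *Cost neutrality will be claimed only if the 95% confidence interval for the between-arm difference in medical cost lies within a margin fixed before analysis.* If no margin can be justified, drop the claim.
- **Behavioural contrasts.** Label costs by quit attempt and by quit status as descriptive.

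The cost is SAP wording and a little more analysis. Delivery costs and abstinence by arm are already to be collected; medical-cost sampling must be set out for both arms. The downside is that neutrality becomes harder to claim, and at this sample size it may be out of reach for a tight margin.

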4.9 Data Analysis Plan

All analyses are based on an intent-to-treat approach, and are nearly identical to analyses from our current and prior studies. Exploratory analysis will be performed on all variables to determine if transformations are needed. Any significant baseline differences between groups will be included in regression analyses described below. All analyses below will be run separately for full intent-to-treat sample (immediately below), per protocol, and, within the NRT group, using those participants who used single vs. combined NRT products.

Examination of Potential Site Differences Outcomes and patient characteristics will be estimated across clinics using summary statistics and confidence intervals. This will be considered an exploratory analysis due to the relatively large number of clinics and, hence, the large number of multiple comparisons that could arise. Grouped logistic regression modeling may be used to describe associations between clinic characteristics and binary clinical outcomes (e.g., quit rate).

Missing Data & Dropout The most conservative approach for handling missing data is to substitute them with baseline values, assuming outcomes have all returned to baseline, with no quit attempts made or abstinence achieved. If this assumption is incorrect, it biases the results towards the null by reducing between group differences. Since we expect few missing data, we will use this approach. If missing data >10%, we will calculate results using this conservative method but also using methods in which missing data are imputed as described in the SRNT guidelines. We will also assess whether dropout is differential by study group. In our current and recent studies of cessation induction, this has not been the case. Abstinence will be reported both with and without (missing samples) cotinine verification.

Hypotheses 1a, 2, & 3 These hypotheses predict that provision of NRT samples will lead to higher abstinence rates (Hyp. 1a), incidence of quit attempts (Hyp. 2), and uptake of additional treatment (Hyp. 3). Logistic regressions will be performed for each outcome with treatment group (standard care vs. NRT sampling)

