as the covariate, estimated using generalized estimating equations (GEE) to account for clustering within clinic. Rates for each outcome will be estimated along with its 95% confidence interval. The coefficient on group will be evaluated using a Wald test to determine if the abstinence rates in the two arms are statistically significantly different at the one-sided 0.025 level. Additional regression modeling will be performed where covariates such as age, gender, and race are accounted for. We will also consider interactions between NRT and categorical covariates to determine if there are certain subgroups in which NRT sampling is more or less effective. Though we expect few individuals to make more than one quit attempt over the span of 6 months, and thus examine incidence of quit attempts (Hypothesis 2), we will examine the distribution of quit attempts, and if appropriate, examine number of quit attempts via Poisson regression modeling. In addition to binary outcomes of treatment uptake (Hyp. 3), we will test for continuous outcomes (e.g., treatment intensity, duration) via GEE regressions.

Hypotheses 1b Hypothesis 1b predicts that provision of NRT samples will result in longer period of abstinence (longest # days non-smoking) across the entire study duration, and will be evaluated using regression modeling via GEE accounting for clustering by clinic.

Secondary Analyses

Provider Acceptability We will provide separate, descriptive data on provider acceptance and satisfaction with treatment delivery. We do not plan any formal between group comparisons because of very limited sample size (14 clinics in each site). This study is not powered on provider-level outcomes of our intervention, but such data will be useful as we consider expanding our intervention into different venues.

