4.10 Quality Assurance Plan

Data will be collected centrally by our research staff rather than locally at each clinic. Computerized data collection methods (Redcap) optimize quality assurance. Redcap system does not accept outliers, illogical response patterns, etc. The PI will have weekly meetings with the research assistants to discuss qualitative comments received during data collection and any problems in data collection. The statistician will periodically examine the database to look for irregularities. Initial data analyses will examine distributions of variable scores, comparability of baseline characteristics, follow-up rates and use of extra-study cessation treatment across conditions in case analyses need to be adjusted for these.

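### Continuous secondary outcomes are planned in two versions with neither named as main, and the outcome's own baseline enters the model only after a significant baseline test (minor; free improvement)

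*Combined protocol and SAP*

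**What the plan says.** Section 4.9, Secondary Analyses, under Other, introduces these outcomes: "We will also examine changes in cigarette smoking, motivation, confidence, attitudes/knowledge of NRT over time, as a function of treatment group". It continues: "These continuous variables (absolute, and change since baseline) will be examined as per Hypothesis 1b above". The Hypothesis 1b paragraph says only that the outcome "will be evaluated using regression modeling via GEE accounting for clustering by clinic". It names no covariate, and nothing ranks the absolute version against the change version.

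Three other statements bear on adjustment:

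- The opening paragraph of Section 4.9: "Any significant baseline differences between groups will be included in regression analyses described below". The analyses under Other come below it, so the rule covers them.
- Section 4.10 says initial analyses will look at "comparability of baseline characteristics, follow-up rates and use of extra-study cessation treatment across conditions in case analyses need to be adjusted for these".
- The paragraph on Hypotheses 1a, 2 and 3 adds: "Additional regression modeling will be performed where covariates such as age, gender, and race are accounted for". The outcome's own baseline is not among the examples.

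Adjustment for the outcome's own baseline is therefore possible under the plan, but it depends on a significance test. The plan does not say which test is used, at what level, or whether it allows for clustering.

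**The concern.** Each of these outcomes has a baseline measurement, because change from it is computed. Using that measurement as a fixed covariate usually gives the most precise comparison. The plan instead offers a version that ignores baseline and a version that subtracts it with a fixed weight of 1, and adds a covariate only when a test happens to be positive.

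Two things are at stake. First, precision is lost on outcomes that the Specific Aims list as secondary. Second, the two versions can give different answers, and no rule says which one counts. With follow-up at 1, 3 and 6 months (Section 4.1) and several analysis sets (Section 4.9), there is room to report the more favourable result. Because clinics are randomised, chance differences at baseline are also larger than the number of participants alone suggests.

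**Working it through.** The plan states no figure to reproduce here. It gives no SD, effect size, correlation or ICC for these outcomes.

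**Inputs from the documents.** "The sample size is 1300 participants" (Section 4.4). Twenty clinics are randomised and half the sample receives NRT (Specific Aims). This gives 1300/2 = 650 per arm and 1300/20 = 65 per clinic.

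**Assumptions.** r = 0.3 to 0.7; ICC = 0.01 to 0.05; equal SDs at baseline and follow-up; one follow-up visit; two-sided 5% tests (z = 1.96).

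**Step 1. Chance imbalance at baseline.** The SE of the baseline arm difference, in SD units, is sqrt(2 × (1 + 64 × ICC)/650):

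- ICC 0: 0.055
- ICC 0.01: 0.071
- ICC 0.05: 0.114

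Given an observed imbalance d, the absolute comparison carries r × d and the change comparison carries −(1 − r) × d. They move in opposite directions and differ by d. Once baseline is a covariate in a linear model, the two versions give the same arm coefficient. So they can disagree only when the rule has not triggered.

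**Step 2. How often the rule triggers.** If the baseline test respects clustering, it is positive in about 5% of trials. If it ignores clustering, the probability is 2 × (1 − Phi(1.96/sqrt(1 + 64 × ICC))):

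- ICC 0.01: 1.96/sqrt(1.64) = 1.53, giving about 13%
- ICC 0.05: 1.96/sqrt(4.20) = 0.956, giving about 34%

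**Step 3. Precision when the rule does not trigger.** Relative variances v are 1 (absolute), 2(1 − r) (change) and 1 − r² (always adjusted). For an effect with 80% power when always adjusted, power = Phi(2.802 × sqrt((1 − r²)/v) − 1.96), where 2.802 = 1.960 + 0.842.

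| r | Variance: absolute / change / adjusted | Power: absolute | Power: change |
|---|---|---|---|
| 0.3 | 1.00 / 1.40 / 0.91 | 76% | 62% |
| 0.5 | 1.00 / 1.00 / 0.75 | 68% | 68% |
| 0.7 | 1.00 / 0.60 / 0.51 | 52% | 73% |

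**Step 4. With the rule applied to the absolute-value model, r = 0.5.** Simulation of 20 clinics of 65, 4,000 trials per setting, gave these SEs of the arm difference (SD units):

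| ICC | Absolute | Change | Always adjusted | Rule, test ignoring clustering | Rule, clinic-level test |
|---|---|---|---|---|---|
| 0.01 | 0.071 | 0.071 | 0.062 | 0.067 | 0.069 |
| 0.05 | 0.115 | 0.113 | 0.098 | 0.101 | 0.110 |

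Power is then approximately Phi(2.802 × SE(adjusted)/SE(rule) − 1.96):

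- ICC 0.01: 0.062/0.067 gives 74%; 0.062/0.069 gives 71%
- ICC 0.05: 0.098/0.101 gives 78%; 0.098/0.110 gives 70%

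The range is about 70% to 78%.

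**The case against.** The strongest reply is that the plan does provide for baseline adjustment. A reader of the Hypothesis 1b paragraph alone might infer that baseline never enters the model. The opening rule of Section 4.9 and the check in Section 4.10 contradict that. A reader might also apply 68% power to the plan as a whole. That figure holds only at r = 0.5 and only when the rule does not trigger. It is also the least favourable r for the better of the two versions: at r = 0.3 the absolute version keeps 76%, and at r = 0.7 the change version keeps 73%. If the baseline test ignores clustering and the ICC is 0.05, the rule recovers most of the loss. These points stand.

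It is also fair to say that the variance ratios are idealised. Cigarette consumption is truncated at entry (at least 5 a day) and is zero for abstainers later, so equal SDs are doubtful for that outcome. The plan follows these outcomes over several visits. For missing data it says: "The most conservative approach for handling missing data is to substitute them with baseline values". This sets those changes to zero and raises the observed r.

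Finally, the outcomes are secondary, with no numbered hypothesis and no stated power. Section 4.9 contains no mediation analysis. The mediator findings in the Abstract and Specific Aims come from the earlier trial, so these comparisons should not be read as this trial's formal test of mechanism.

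None of this supplies a main version, or a reason to make a useful covariate depend on a significance test.

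**Conclusion.** The point holds as a minor one. Each outcome has two planned versions with no main one, and its own baseline is adjusted for only if a baseline test is significant. If that test respects clustering, about 95% of trials would go unadjusted. Under the equal-SD, single-visit assumptions, a model that always includes baseline is at least as precise as either planned version. Its variance is 9% to 49% lower than the absolute version and 35% to 15% lower than the change version as r goes from 0.3 to 0.7. The size for this trial is not known, because the documents give neither r nor ICC.

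A reader might infer that the planned estimates are biased. They are not: under randomisation both versions are unbiased, and a chance imbalance is noise. A reader might also infer that the trial's main result is at risk. It is not, because the 6-month abstinence comparison does not use these analyses.

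**What to change.** In Section 4.9, under Other, replace the parenthesis naming two versions with one main analysis per outcome: the follow-up value regressed on arm and that variable's own baseline, in the clinic-clustered GEE. State that the baseline term is always included, whatever the baseline comparison in the opening paragraph shows. Name the 6-month visit as the main time point, or fit the 1-, 3- and 6-month visits jointly with the baseline covariate. Report mean change by arm descriptively.

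This costs two or three sentences. It needs no new data and reduces the number of analyses.
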